7.5.7 Evaluation of Target Lesions

Table 7-2 summarizes the response evaluation by serial imaging using imRECIST. In patients with progressive disease, particularly on the first scan, it is recommended to confirm disease progression with a subsequent scan at least 4 weeks later. If the subsequent scan shows no progressive disease (lack of confirmation), patient would not be captured as having a progressive event and may continue on therapy per protocol. In patients with unequivocal disease progression as determined by the treating investigator, a confirmatory scan will not be required. In this situation, patient would discontinue therapy on study and be captured as a progressive event.

Table 7-2. Response evaluation by imRECIST:

Complete Response (CR)
	
Disappearance of all target lesions. Any pathological lymph nodes (whether target or non-target) must have reduction in short axis to <10 mm. To be assigned a status of complete response, changes in tumor measurements must be confirmed by a repeat assessment performed no less than six weeks after the criteria for response is met. This can be performed at the next scheduled scans per protocol. Patients must also have complete disappearance or normalization of lymph nodes/other non-target tumor sites (e.g. resolution of a malignant pleural effusion), and no new non-measurable lesions.

Partial Response (PR)
	
At least a 30% decrease in the sum of the diameters of target lesions, taking as reference the baseline sum diameters, as well as the addition of new measurable lesions. To be assigned a status of partial response, changes in tumor measurements must be confirmed by a repeat assessment performed no less than six weeks after the criteria for response is met. This can be performed at the next scheduled scans per protocol. Patients must also not have unequivocal progression in non-target lesions and new lesions.


Progressive Disease (PD)
	
At least a 20% increase in the sum of the diameters of target lesions, taking as reference the baseline tumor assessment. New measurable lesions will be added to the total sum of diameters calculation (numerator). This will be used for assessment of best overall response. In patients with tumor burden decrease followed by tumor burden increase, the nadir sum of diameters will be used for assessment of progression (i.e. the new denominator). If this occurs, an increase of 20% from nadir will used for determination of progression. The sum must also demonstrate an absolute increase of at least 5 mm. Subjects with equivocal disease progression (e.g. a new lesion in the setting of major disease regression and the absence of or improvement in disease related symptoms) should have a scan confirming disease progression at least 4 weeks following the initial scan showing imRECIST defined PD. Subjects may continue on protocol therapy until repeat scan confirms PD. If repeat scan does not confirm PD, subjects should proceed with treatment and evaluation as directed by the protocol.

Stable Disease (SD)	Neither sufficient shrinkage to qualify for PR nor sufficient increase to qualify for PD, taking as reference the smallest sum diameters while on study. NOTE: a change of 20% or more that does not increase the sum of the diameters by 5 mm or more is coded as stable disease). To be assigned a status of stable disease, response must be confirmed on a subsequent scan.
---------------------	---

The best overall response is the best response recorded from the start of the treatment until disease progression/recurrence or non-protocol therapy (taking as reference for progressive disease the smallest measurements recorded since the treatment started). The patient's best response assignment will depend on the achievement of both measurement and confirmation criteria. Table 7-3 summarizes potential outcomes.

Table 7-3. Summary of potential response outcomes by imRECIST

Target Lesions and New Measurable Lesions	Non-Target Lesions	New Lesions (Non-measurable)	Overall Response
CR	CR	No	CR
CR	Non-CR/Non-PD	Yes or No	PR
PR	Non-PD	Yes or No	PR
SD	Non-PD	Yes or No	SD
PD	Any	Yes or No	PD
Any	PD (unequivocal)	Yes or No	PD

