2.0 INTRODUCTION

Combination immune checkpoint blockade with nivolumab and ipilimumab demonstrated objective responses in 58% of patients with advanced unresectable melanoma in the Checkmate 067 study [1]. While responses and progression free survival (PFS) are superior with nivolumab/ipilimumab over monotherapy, not all patients have long-term benefit. Twenty four percent of patients had progressive disease as their best response and over 30% of patients progressed after initial disease control. At one year, the PFS rate was 49%. In addition, several patient subgroups had less clinical benefit as demonstrated by shorter progression free survival in patients with PD-L1 low tumors, high LDH levels, M1c disease, or greater than 3 disease sites. Other studies have also shown that patients with low interferon gamma gene expression scores or low baseline tumor immune infiltrate are less likely to have a response to standard anti-PD-1 based therapy [2]. Therefore, further immunotherapy strategies are needed.

Targeting vascular signaling in the tumor microenvironment, along with other oncogenic pathways, can enhance the anti-tumor activity of immune checkpoint therapies. A phase 1 study ipilimumab in combination with the anti-VEGF antibody bevacizumab in patients with advanced melanoma demonstrated an increased response rate and longer median overall survival compared to historical data [3]. On-treatment tumor biopsies revealed activated vessel endothelium with extensive CD8+ and macrophage cell infiltration. Similarly, clinical trials of combination therapy with the VEGFR inhibitor axitinib plus pembrolizumab and bevacizumab plus atezolizumab have demonstrated markedly increased anti-tumor activity in patients with advanced renal cell carcinoma [4, 5]. In addition to increased immune cell infiltration, targeting VEGF/R can enhance T-cell priming and dendritic cell maturation, as well as increased MHC class antigen presentation on tumor cells, which can lead to greater anti-tumor immune responses [6-8].

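### Because stable disease needs a confirming scan, a subject controlled at week 13 who progresses at week 25 is scored PD or gets no best-response category

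*Combined protocol and SAP*

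**What the plan says.** Section 7.5 uses imRECIST for response and PFS and says that the best overall response rate will be reported. A subject with measurable disease at baseline who has received at least one dose of each drug counts as evaluable after one on-treatment scan or clinical progression.

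On **confirmation**, the SD row of Table 7-2 (Section 7.5.7) states: "To be assigned a status of stable disease, response must be confirmed on a subsequent scan". It gives no minimum interval. CR and PR need a repeat assessment at least six weeks later. Below the table: "The patient's best response assignment will depend on the achievement of both measurement and confirmation criteria".

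On the **PD reference**, the PD row begins: "At least a 20% increase in the sum of the diameters of target lesions, taking as reference the baseline tumor assessment". It adds new measurable lesions to the sum and continues: "This will be used for assessment of best overall response". It then says that after a decrease the nadir is the reference for progression. The paragraph below the table defines best overall response "taking as reference for progressive disease the smallest measurements recorded since the treatment started". The SD row also uses the smallest sum on study.

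Table 7-3 lists four overall outcomes: CR, PR, SD and PD. The Synopsis and Table 7-1 set tumor imaging every 12 weeks, with on-treatment scans at week 13 and then week 25.

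**The concern.** With this schedule, the first planned scan that can confirm a week-13 SD is the week-25 scan. If that scan shows PD, the SD is never confirmed. The subject had disease control at the first assessment, yet the only categories left are PD or nothing. The same holds for a PR at week 13 that is lost by week 25: it is neither a confirmed PR nor a confirmed SD.

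At stake is the reported split of best overall response between SD, PD and missing. Subjects with early control would be pooled with subjects who never had it. Because the PD reference can be read in two ways, two assessors could also score the same record differently.

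**Working it through.** The plan states no figure for this point, so the check applies the written rules to example records.

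**Rules used (Table 7-2).** PD: rise of at least 20% and at least 5 mm over the reference. PR: fall of at least 30% from baseline, confirmed. SD: neither PR nor PD, judged against the smallest sum, confirmed on a later scan. Week-25 PD is taken as standing, with no scan between weeks 13 and 25.

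| Sums, mm (baseline / week 13 / week 25) | Week 13 | Week 25 vs baseline | Week 25 vs smallest sum | Best response, baseline reference | Best response, smallest-sum reference |
|---|---|---|---|---|---|
| 100 / 95 / 125 | SD | +25% | 125/95 = +32% (+30 mm) | PD | PD |
| 100 / 65 / 85 | PR, unconfirmed | −15% | 85/65 = +31% (+20 mm) | none | PD |
| 100 / 75 / 95 | SD | −5% | 95/75 = +27% (+20 mm) | none | PD |
| 100 / 90 / 95 (control) | SD | −5% | 95/90 = +6% (+5 mm) | SD | SD |
| SD at week 13, no later scan | SD | – | – | none | none |

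In rows 2 and 3 the baseline reference does not give PD. SD is not available either, because the SD row itself uses the smallest sum and the week-25 rise exceeds 20% over it. Hence no category.

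**Effect of each repair.** Using the smallest sum throughout, but keeping SD confirmation, removes the empty cells in rows 2 and 3 but scores both records PD. It does not help the last row. Dropping SD confirmation and counting an unconfirmed PR as SD gives SD in rows 1, 2, 3 and 5 under either reference.

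**Possible size.** The documents do not give the share of subjects controlled at week 13 who progress by week 25. Two assumed patterns give a range.

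- *Background figures in Section 2.0.* Assume that the 24% with PD as best response all progressed by the first scan (12 weeks), that 49% are progression free at 52 weeks, and that the hazard is constant between. Then h = ln(0.76/0.49)/40 = 0.01097 per week; S(24) = 0.76 × exp(−12 × 0.01097) = 0.666; 0.76 − 0.666 = 0.094, and 0.094 × 23 = 2.2 subjects.
- *Exponential PFS*, S(t) = p^(t/52). At p = 0.50: 0.852 − 0.726 = 0.126, or 2.9 of 23. At p = 0.75: 0.936 − 0.876 = 0.060, or 1.4 of 23.

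The range is about 1 to 3 of 23. It counts all PFS events in the interval, deaths included, so it leans high for scan-based PD. It leaves out subjects with SD at week 13 and no later scan.

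**The case against.** **The two PD references can be reconciled.** The PD row itself moves to the nadir after a decrease, and without a decrease baseline is the smallest sum. The sentence "This will be used for assessment of best overall response" follows the one on new measurable lesions, so it may refer to that enlarged sum rather than to the baseline reference. This stands: the wording is ambiguous, and a flat contradiction is only one reading. Under the reconciled reading, however, all three progression examples become PD, so the SD problem remains.

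**The week-13 SD could be taken as the best response recorded before progression.** The sentence making assignment depend on confirmation rules that out.

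**An unscheduled scan could confirm SD.** True, because no interval is set. So not every subject who progresses at the second planned scan is affected.

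**Requiring confirmed SD is a legitimate choice, since it excludes brief stability.** That is fair, but the plan then needs a category for the subjects it excludes, and Table 7-3 has none.

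**Nothing planned depends on it.** A reader might infer that the regimen would look worse on primary resistance than the historical control, because Section 2.0 reports separately: "Twenty four percent of patients had progressive disease as their best response and over 30% of patients progressed after initial disease control". The documents do not support that inference. The 24% is background; Section 11 uses only the 1-year PFS rate as historical control, and no PD-share or disease-control endpoint is defined. The historical scan schedule is not given. Even a shift from 6/23 to 8/23 would move between exact 95% intervals of 10–48% and 16–57%. A reader might also infer harm to the biomarker work, but Sections 4.0 and 7.6.1 name ORR, PFS and OS as its outcomes. These limits stand. It is also possible that the best overall response rate in Section 7.5 means only ORR, in which case less is at stake.

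**Conclusion.** The point holds as a minor defect in a reported result. As written, SD or an unconfirmed CR or PR at week 13 followed by PD at week 25 cannot be scored SD. It becomes PD or, under the baseline reading, may have no category. SD at week 13 with no later scan has no category at all, although the subject is evaluable.

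The definitional finding assumes only that there is no extra scan between weeks 13 and 25. The size, about 1 to 3 of 23 subjects, rests on the assumed progression patterns shown and is not a figure from the plan.

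The effect is confined to SD versus PD or missing. It should not be read as a threat to the primary analysis: progression is judged against the nadir, so the 1-year PFS count does not move. ORR does not move because CR and PR have their own confirmation rule and SD is not a response. OS does not use response categories.

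**What to change.** In Table 7-2, replace the sentence requiring confirmation of SD with: *SD is assigned when SD criteria are met at the first scheduled on-treatment scan or later; no confirmation is required; an unconfirmed CR or PR counts as SD.*

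State one PD reference for both best response and progression: the smallest sum on study, including baseline. Reword the PD row to match, but keep the statement that new measurable lesions are added to the sum.

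The cost is a wording change in one table, with no new data or scans, best made before best response is scored. The downside is that the SD share will include short-lived stable disease; the PFS curve already shows how long control lasted.

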7.6 Correlative studies

7.6.1 Biomarkers

A variety of factors impact the immunomodulatory properties and efficacy of immune checkpoint therapy, including nivolumab and ipilimumab, in patients with advanced melanoma. Baseline variables and changes that occur during treatment can be used to predict anti-tumor immune responses and to correlate with mechanisms of action of agents with immune modulatory properties, such as the RTK inhibitor cabozantinib. These include tumor specific factors such as tumor mutational burden, PD-L1 expression, MHC antigen presentation, interferon gamma related gene expression profiles [2, 34]. Host factors such as baseline peripheral lymphocyte counts, inhibitor immune cell levels (such as Tregs), HLA variants and dynamic changes during treatment have also been associated with responses to immune checkpoint therapy responses. Recent data on the gut microbiome indicates this may play a large

role in anti-tumor immunity as well [35]. In addition, anti-VEGF/R and anti-c-MET therapies have the ability to enhance T-cell priming and dendritic cell maturation, increase MHC antigen presentation on tumor cells, reduce immune suppressive Treg and myeloid cell populations, and activate vessel endothelium that can lead to augmented CD8+ T-cell and macrophage cell infiltration [4-8, 10, 11].

Assessment of baseline and on treatment molecular and cellular variables will serve the purpose of establishing predictive biomarkers for nivolumab/ipilimumab plus cabozantinib in patients with advanced melanoma. Exploratory analyses and comparisons to efficacy endpoints – ORR, PFS, and OS will be performed. In particular, this data will allow identification of sub-populations where clinical benefit is most often observed. We hope to show that patients typically predicted to have a low probability of response (e.g. PD-L1 IHC <1%, interferon gamma GEP low) will have substantial clinical benefit with the immunotherapy strategy investigated in this protocol. This will lead to future studies of nivolumab/ipilimumab plus cabozantinib in biomarker selected advanced melanoma patients.

Collection time points of biospecimens on protocol is outlined in Table 7-1. Refer to lab manual for specific details on handling, processing, and storage of biospecimen samples. Future assays planned for tumor specimen biomarker analyses include targeted exome sequencing (or whole exome sequencing), RNA gene expression, PD-L1 immunohistochemistry, and multiplex immunofluorescence for assessment of immune cell populations and immune markers. Peripheral blood will be analyzed by flow cytometry to characterize dynamic changes in immune cell populations, along with assessment of cytokines and other variables. Stool microbiome will be analyzed by 16s rRNA sequencing or equivalent approach. Additional biomarker analyses may be considered based on emerging data.

Samples remaining after initial protocol specific testing is completed will be banked for future unspecified cancer related research. Permission from subjects will be obtained during the consenting process. Samples that are collected will be identified by a subject's sequence ID number assigned at the time of registration to the trial. Any material issued to collaborating researchers will be anonymized and only identified by the subject's study number.

8 TREATMENT PROCEDURES

8.1 Composition, Formulation, and Storage

At study sites, all study medication will be stored as described in the appropriate prescribing information for that country (if applicable) or the pharmacy manual and inventoried in accordance with applicable state and federal regulations.

8.2 Investigational Treatment: Cabozantinib

Cabozantinib tablets are supplied as film coated tablets containing cabozantinib malate equivalent to 20 mg of cabozantinib and contain microcrystalline cellulose, lactose anhydrous, hydroxypropyl cellulose, croscarmellose sodium, colloidal silicon dioxide, magnesium stearate and Opadry® yellow. The 20-mg tablets are round. Doses of 40 mg will comprise two 20-mg tablets. The components of the tablets are listed in Table 8-1.

- Dose reductions or interruptions may also occur in the setting of lower grade toxicity than defined in Table 8-3, if the investigator feels it is in the interest of a subject’s safety and will optimize drug tolerability.
- Interruption of cabozantinib treatment for cabozantinib-related AEs may occur at any time per investigator discretion. If treatment is interrupted due to related AEs for more than 6 weeks, cabozantinib should be discontinued unless there is unequivocal evidence that the subject is benefitting. In this situation, a subject may be able to restart therapy with a dose reduction upon resolution of the toxicity per the discretion of the investigator.
- Dose interruptions for reason(s) other than related AEs (eg, surgical procedures) can be longer than 6 weeks per the discretion of the investigator.

Guidelines for the management of specific AEs are provided in Section 8.2.4.

Table 8-2: Dose Reductions of Cabozantinib

Assigned Dose	First Dose Level Reduction	Second Dose Level Reduction
40-mg cabozantinib oral qd qd, once daily	20-mg cabozantinib oral qd	No dose reduction permitted

Cabozantinib will be discontinued if a qd dose of 20-mg cabozantinib (minimum dose) is not tolerated

Table 8-3: Dose Modifications of Cabozantinib for Treatment-Related AEs

CTCAE v.4.0 Grade	Recommended Guidelines for Management^a
Grade 1 AEs	Add supportive care as indicated. Continue cabozantinib treatment at the current dose level if AE is manageable and tolerable.
Grade 2 AEs which are tolerable and are easily managed	Continue cabozantinib treatment at the current dose level with supportive care.
Grade 2 AEs which are intolerable and cannot be adequately managed	At the discretion of the investigator, cabozantinib should be dose reduced or interrupted. Note: It is recommended that dose holds be as brief as possible.
Grade 3 AEs (except clinically non-relevant laboratory abnormalities)	Cabozantinib should be interrupted unless the toxicity can be easily managed with a dose reduction and optimal medical care. Note: It is recommended that dose holds be as brief as possible.
Grade 4 AEs (except clinically non-relevant laboratory abnormalities)	Subjects should have cabozantinib interrupted immediately. Discontinue cabozantinib unless the following criteria are met: 
 • Subject is deriving clear clinical benefit as determined by the investigator • Toxicity can be managed with a dose reduction following recovery to Grade 1 (or baseline) and optimal medical care

AE, adverse event.

Note: The dose delay and modification criteria for specific medical conditions are provided in Section 8.2.4 . For re-treatment criteria of study treatment after a dose hold see Section 8.2.3.

^a Study treatment dose adjustment is only needed if the toxicity was deemed related to cabozantinib treatment or had an unclear relationship to cabozantinib treatment.

8.2.3 Cabozantinib Dose Reinstitution and Reescalation

If the subject recovers from his or her toxicities to CTCAE v.4.0 Grade \leq 1 or to the baseline value (or lower) and the toxicity was unrelated to study treatment, then study treatment may be restarted with no change in dose.

If the subject recovers from his or her toxicities to Grade \leq 1 or to the baseline value (or lower) the toxicity was deemed possibly related to study treatment, then study treatment may be restarted at a reduced dose (see Table 8-2 for the schedule of dose reductions).

Subjects receiving a daily dose of 20 mg may be restarted at the same dose if deemed safe at the discretion of the investigator. Subjects unable to tolerate a daily dose of 20 mg should discontinue study treatment.

Re-escalation to the previous dose, (but not higher than 40 mg/day) may be allowed at the discretion of the investigator for AEs which have resolved or recovered to Grade 1 (or baseline value) and deemed tolerable and easily managed by optimized supportive treatment. Dose re-escalation is not allowed for a drug-related dose reduction triggered by Grade 4 hematologic toxicities or by Grade 4 AEs affecting major organs (eg, central nervous system, cardiac, hepatic, renal).

8.2.4 Guidelines for Management of Potential Adverse Events associated with Cabozantinib

Subjects will be monitored for AEs from the time of signing informed consent through their last follow-up visit (30 days after the date of the last dose of cabozantinib treatment.) Subjects will be instructed to notify their physician immediately at the onset of any AE. Seriousness, severity grade, and relationship to study treatment of AEs will be determined by the investigator. AE severity will be graded by the investigator in accordance with CTCAE v.4.0. Management of severe or intolerable adverse reactions may require temporary dose reduction and/or interruption for cabozantinib.

8.2.4.1 Cabozantinib Adverse Events

The most frequent AEs experienced by $\geq 20\%$ of subjects treated with cabozantinib in descending order of frequency were diarrhea, fatigue, decreased appetite, nausea, weight decreased, PPES, vomiting, constipation, hypertension, dysgeusia, dysphonia, asthenia, and dyspnea. For a full description of the safety profile of cabozantinib, refer to the Cabozantinib Investigator's Brochure.

Other medically important but less frequent AEs including arterial thrombotic AEs (eg, transient ischemic attack [TIA], and myocardial infarction [MI]) and venous thrombotic AEs (eg, deep vein thrombosis [DVT] and pulmonary embolism), severe hemorrhagic events, proteinuria, wound healing complications, gastrointestinal (GI) perforation, abscesses including intra-abdominal and pelvic abscess, GI and non-GI fistula formation, osteonecrosis, and reversible posterior leukoencephalopathy syndrome (RPLS).

Adverse events associated with laboratory abnormalities experienced by $\geq 5\%$ of subjects treated with cabozantinib in descending order of frequency were anemia, AST increased, ALT increased, hypothyroidism, hypokalemia, hypomagnesemia, thrombocytopenia, hypocalcemia, hypophosphatemia, lactate dehydrogenase (LDH) increased, lipase increased, neutropenia, hyponatremia, ALP increased, leukopenia, and hyperglycemia.

Adverse events may occur within the first few weeks in the course of treatment with cabozantinib, as cabozantinib is expected to reach steady state exposure at approximately 2 weeks following first dose. Events that generally have an early onset include hypocalcemia, hypokalemia, thrombocytopenia, hypertension, PPES, abdominal pain, mucosal inflammation, constipation, diarrhea, and vomiting. Adverse events should be managed with supportive care at the earliest signs of toxicity. Dose reductions and treatment interruptions should be considered. Dose reductions are recommended for events that, if persistent, could become serious or intolerable (Section 8.2.2).

Cabozantinib should be discontinued for the following AEs: visceral perforation or fistula formation, severe hemorrhage, serious arterial thromboembolic events, nephrotic syndrome, hypertensive emergency, persistent uncontrolled hypertension despite optimal medical management, and RPLS.

